1.4 Synopsis of Protocol

[figure not shown]
title of Trial:	Prioritization and Optimisation of Multimедication in elderly, multimorbid patients in general practice
Abbreviated name of trial	PRIMUM Pilot - Pilot trial on Prioritization of Multimедication in Multimorbid patients
Sponsor	Johann Wolfgang Goethe University, Frankfurt am Main
Head of Clinical Trial	Dr. med. [name]
Indication:	Multimедication in elderly, multimorbid patients: Age ≥ 65 , ≥ 3 chronic diseases, ≥ 5 long-term medicines
Rationale	
 1. Multimorbidity, multimедication and increasing age raise the risk of inappropriate prescriptions and adverse drug events 2. Multimедication and high complexity of medication reduce adherence among patients 3. Doctor patient interviews on problems related to medicines are dominated by doctors in content and focus mostly on effectiveness 4. Patients do not generally inform doctors of adverse drug reactions and autonomous decisions to adjust medication dose 
(1) Use of pharmaceutical information system (AiD+) reduces number of inappropriate prescriptions (pharmaceutical interactions, renal dose adjustments, duplicate prescriptions)
 
(1-4) Take records of medicines that were actually taken and problems relating to medicines (technical handling, potential adverse drug reactions) by medical assistant provides structured information for the family doctor and enables patients to discuss their problems with the doctor.
 
→ Prescriptions become more appropriate → Prescriptions become less complex → Prescriptions take the patient's perspective into account (avoidance of adverse drug reactions, patients' preferences are taken into account) and prioritised → Patients are more satisfied with the information they receive and adhere to the doctor's therapy

Trial design:	Pilot trial, two armed, controlled, open, cluster-randomized (Randomization and intervention on the general practice level (HA-Praxen), measurement of outcomes on patient level, blind evaluation
Aim of trial:	
 (1) To ascertain the feasibility of an intervention for the prioritization and optimisation of multimедication in elderly, multimorbid patients in general practice (2) To investigate the feasibility of the planned cluster-randomized main trial for the evaluation of the effectiveness of this intervention under the following aspects: 
 - The practicability of the intervention, - The recrutability of practices and patients, - The randomisability of practices,

	
 - A check of the suitability of the Medication Appropriateness Index as a potential, primary outcome criterium for the planned main trial and, based on that, the sample size estimation for the main trial.
Further aims of the trial:	
 - To investigate the suitability of further target variables for the main trial; - A description of usual care among family doctors when adjusting medication for elderly, multimorbid patients
Number of trial sites and patients	To test a criterium, 30 patients per group are sufficient for a good estimate of mean and standard deviation. In order to achieve this aim with certainty, 50 patients will be recruited for the intervention group and 50 for the control group, making a total of N=100. Therefore five patients will be recruited from each of k=20 practices.
In- and exclusion criteria for trial sites (practices)	
Inclusion criteria
 
 - Doctor's practice accepts patients covered by statutory health insurance - Active in primary care - Specialist doctor for general practice or internal medicine, or doctor with no specialist field. - Practice has internet access - Investigator's agreement to fulfil the contractual obligations arising from the trial - Agreement of the investigator to train a medical assistant from the practice for the intervention, as required by the trial (brown bag review, patient interviews on basis of checklist) 
Exclusion criteria
 
 - Practice focuses on unconventional medical treatments - Practice focuses on special indications (e.g. HIV)
In- and exclusion criteria for patients	
Inclusion criteria:
 
 - Age ≥ 65 and - ≥ 3 chronic diseases - ≥ 5 long-term medicines and - Health care provided by family doctor (at least one contact in most recent quarter) and - Ability to understand and participate in trial of own free will, to fill out questionnaires and participate in telephone interviews as well as - Written consent to participate in trial 
Exclusion criteria:
 
 - Diseases cause life expectancy of < 6 months - Abuse of alcohol or illegal drugs and visible clinical signs or symptoms thereof - Cognitive disability that prevents trial participation (MMSE < 26) or - emotional stress that prevents participation in trial or - not legally competent or - Participation in a clinical investigation over the following 30 days - -

Therapy	Intervention: computer assisted optimization of multi-medication using recommended standard controls: Usual care in accordance with recommended standards
Visits:	Visit T0 (Baseline), Visit T1 (Follow up after 6 weeks), visit T2 (Follow up after 12 weeks)
Primary and secondary outcomes:	
A) Practicability of intervention
 
 ▪ Estimation of time / cost of intervention including training for GPs and medical assistants 
B) Feasibility of trial
 
 ▪ Reasons for non-participation of patients ▪ Proportion of patients with loss to follow up compared to entire population ▪ Feasibility of taking measurements T0, T1 (Time required by GP and medical assistant for documentation, content and duration of patient interviews) 
C) Test potential outcome criteria for the main trial:
 
 1. Appropriateness of medication (potential primary outcome criterion in the main trial): the appropriateness will be rated by two experts independently and blinded with regard to the group to which the patient belongs by means of the Medication Appropriateness Index (MAI) and selected scales from the PiDoc®-classification system. The feasibility (quantity of trial data required, time consumed by medication review) will be checked and the effect size of the intervention will be calculated before and after, as well as between groups. 2. Medication complexity: 
 ▪ Sum of prescriptions ▪ Number of single doses / day ▪ Complexity of the medication regimen (Medication Regimen Complexity Index, MRCI) 3. Adherence and other factors 
 ▪ Adherence as observed from discrepancies between intake (patient interviews) and the prescription (doctor's documentation) at T0, T1 and T2. 
 - Discrepancy score, DIS (Sum of all discrepancies in medicine, time of intake, frequency and dose / sum of all prescriptions, DIS >0.2=1 - Overestimate/Underestimate of actual intake by doctor: Drug Score (DS, Sum of all drug intake / sum of all prescriptions) DS<0.8 or DS>1.2=1. - Dose Score (DoS): $DoS = d1(a1) + d2(a2) + d3(a3) + \dots / n$ d = patient's intake (0.1) of prescribed medicines, n = sum of all prescriptions, a = variance (actual dd intake/prescribed dd); DoS<0.8 or DS>1.2=1. - Regimen Score (RS): $RS = d1(b1) + d2(b2) + d3(b3) + \dots / n$ d = patient's intake (0.1) of prescribed medicines, n = sum of all prescriptions, b = variance (actual intake frequency per day / prescribed frequency per day); RS<0.8 or DS>1.2=1. ▪ Self reported adherence of patients (Medication Adherence Report Scale, MARS and adherence according to Morisky) ▪ Attitude of patients to medicinal therapy (Beliefs about Medicines Questionnaire, BMQ)

	
 ▪ Satisfaction of patients with information provided on medicines 4. Quality of life, preservation of functional status ▪ General quality of life (EuroQuoL) ▪ WHO Disability Assessment Schedule (WHO-DAS II) 5. Pain ▪ Verbal Rating scale (VRS) 6. Days in hospital 7. Number (and type) of adverse drug reactions(ADR)
Potentially disruptive factors	
 ▪ Age ▪ Gender ▪ Additional prescribers in treatment process ▪ Depressivity (Geriatric Depression Scale, GDS) ▪ Co-morbidity: Cumulative Illness Rating Scale (CIRS), Charlston-Comorbidity-Index ▪ Infirmity (Sherbrooke Questionnaire)
Biometrics	
 - Descriptive and according to the intention to treat principle - Additional evaluation per protocol in form of sensitivity analyses - Regression for effects of covariables - All analyses include correction for cluster effect
Schedule:	
 - Begin of pre-phase for the development of Drug Information Service +, all trial plans and implemented instruments 01.01.09 - Begin of practice recruitment 01.02.09 - Begin of trial (sponsorship begins) 01.03.09 - Vote from Ethics Commission 16.03.09 - Begin of patient recruitment 01.05.09 - Duration of trial three months per patient - Deadline for interim report 01.12.09

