In consequence it is to be expected that patients are more satisfied with the information they have received on their medication and are more likely to adhere to the doctor's instructions. Their health can be improved through the avoidance of undertreatment in pain therapy and possibly through a reduction in adverse drug reactions and associated events. As a result their functional situation and general quality of life should be improved.

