4.1.2 Secondary outcomes

Secondary outcomes are:

1) *Change in MAI score after 12 weeks*

- Difference between base value (T0) and value after 12 weeks (T2)

2) *Change in complexity of medication after 6 and 12 weeks*

- Total number of prescriptions
- Number of single doses / day
- Medication regimen complexity (Medication Regimen Complexity Index, MRCI)

3) *Change in adherence and associated variables*

- Observed adherence measured as the difference between intake (*brown bag review*) and prescribed medication (physician's records) after 6 to 12 weeks.
 - o Discrepancy score, DS (Sum of all differences in drug, time of intake, frequency and dose) / Sum of all prescriptions, $AS > 0.2 = 1$
 - o Overestimate / underestimate of actual intake by the doctor:
Drug Score (DS, Sum of all drugs taken/sum of all prescriptions), $DS < 0.8$ oder $DS > 1.2 = 1.31$
 - o Dose Score (DoS)
 $DoS = d1(a1) + d2(a2) + d3(a3) + \dots / n$

d = Patient intake (0.1) of prescribed medication

n = Sum of all prescriptions

a = Discrepancy rate (actual intake dd / prescribed dd)

DoS<0.8 or DS>1.2=1.31

o Regimen Score (RS)

RS = d1(b1) + d2(b2) + d3(b3) + ... /n

d = Patient intake (0.1) of prescribed drugs

n = Sum of all prescriptions

b = Discrepancy rate (actual frequency of intake per day / prescribed frequency of intake per day)

RS<0.8 oder DS>1.=1.31

- Change in reported patient adherence (Medication Adherence Report Scale, MARS) *after 6 and 12 weeks*
- Change in the attitude of patients to medicinal therapy (Beliefs about Medicines Questionnaire, BMQ) *after 6 and 12 weeks*
- Change in patient satisfaction with information received on medicines *after 6 and 12 weeks*

4) *Change in quality of life and maintenance of functional status after 6 and 12 weeks*

- Change in general quality of life (EuroQuoL)
- Change in or maintenance of functional status in accordance with WHO Disability Assessment Schedule (WHO-DAS II)

5) *Change in intensity of pain after 6 and 12 weeks*

- Verbal rating scale (VRS)

6) *Days in hospital for whatever reason*

7) *Death for whatever reason*

8) *Adverse drug reaction (ADR)*

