4	Medical assistant enters “house medication” into Medibox 2 brown bag review	
The medical assistant logs into the password protected area of AiD+ and opens the patient’s file (compare patient ID and date of birth with the data in the investigator’s file).
 
The medical assistant enters all drugs, regular medication, necessary medication, prescriptions from co-treating doctors, OTC products including phytopharmaceuticals and nutrition supplements. She enters every drug using its trade name, the name of the active ingredient or National Drug Code. In addition she records the dosage and the name of the doctor who prescribed the drug. Where possible the entry should be simplified by scanning the barcode using a document reader. After entering the information she stores it under home medication (Medibox 2)
 
She prints the results from AiD+ from “Practice medication” (Medibox 1)

	Procedural step	Content
		and "Home medication" (Medibox 2) and logs out of AiD+.
5	The GP checks the medication and problems associated with the medication with the support of AiD+ and MediMoL	The GP logs into the password protected area of AiD+ and opens the patient's file. He checks AiD+, "home medication" and "practice medication" for agreement in terms of the active ingredient (on the ATC code level) and dose (possibly using the pages printed out by the medical assistant). Both home and practice medication appear in a shared AiD+ window (Medibox 3: "coordinated medication", sorted according to ATC group (groups of active ingredients), whereby the origin of the medication – whether home or practice medication – can be recognized by the coloured background. Thus if there is total agreement between home and practice medication (the prescribed medication is the same as the medication actually taken), Medibox 3 will contain drug pairs with identical active ingredients. The GP then deletes the drug pairs and checks the warnings (drug interactions, duplicate prescriptions) and pointers (renal dose adjustment, tablet divisibility, exceeding maximal dose) for clinical relevance. He identifies patient problems using MediMoL. He prepared necessary therapy adjustments in „Medibox 3“.
6	Medical assistant prepares interview between doctor and patient	The medical assistant prepares the AiD+-printouts and the completed MediMoL for the consultation.

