7	Consultation between GP and patient on medication	The GP discusses the identified problems and any necessary changes in the medication with the patient. He saves the prescription plan he has discussed with the patient in the practice computer and makes a note of other arrangements (further appointments, transfer to a specialist etc.) on the Medimol. He ends the interview with the patient and gives the MediMoL back to the medical assistant.
8	Medical assistant enters information into Medibox 3 ("coordinated medication) and ends the intervention	
The medical assistant prints out the updated prescription plan from the practice computer and gives it to the patient. She follows any other instructions that have been made on MediMoL by the GP (e.g. makes an appointment for further interviews, laboratory checks, transfers to a specialist).
 
The medical assistant logs into the password protected area of AiD+, opens the patient's file, checks "Medibox 3" using the current practice prescription plan and makes any necessary changes. She gathers up all documentation on the intervention (printouts of all 3 Mediboxes and the completed MediMoL and places them in the investigator's file. .

9	GP concludes intervention	Finalization of "Medibox 3" ("coordinated medication")

**The inclusion of the central pharmaceutical number serves to ensure data validity*

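### The observed-adherence scores measure agreement between the GP's list and intake, so they can improve in the intervention arm when only the list changes

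*Protocol*

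**What the plan says.** Outcome C3 in the Protocol synopsis (1.4) describes "Adherence as observed from discrepancies between intake (patient interviews) and the prescription" in the doctor's documentation, assessed at T0, T1 and T2. Section 4.1.2, item 3, uses the same idea, "Observed adherence measured as the difference between intake" and the physician's records, under a title announcing change in adherence and associated variables. Four scores follow, all with the number of prescriptions as denominator:

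- **DIS:** "Discrepancy score, DIS (Sum of all discrepancies in medicine, time of intake, frequency and dose / sum of all prescriptions, DIS >0.2=1".
- **DS:** "Overestimate/Underestimate of actual intake by doctor: Drug Score (DS, Sum of all drug intake / sum of all prescriptions", flagged below 0.8 or above 1.2.
- **DoS and RS:** the average, over prescriptions, of actual over prescribed dose (DoS) or frequency (RS), with the same bounds.

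The doctor's side of the comparison is the current-medication part of the CRF (9.3.4.3), completed at all three visits in both arms (1.6).

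In the intervention arm (8.1), step 4 records everything the patient takes. In step 5 the GP checks home against practice medication "for agreement in terms of the active ingredient (on the ATC code level) and dose". In step 7, after the consultation, "He saves the prescription plan he has discussed with the patient in the practice computer". Steps 8 and 9 print the updated plan and finalise the coordinated list. Control practices continue usual care without AiD+ or MediMoL (8.2).

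The Rationale (2.3) states what adherence is meant to capture: patients who "are more likely to adhere to the doctor's instructions".

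**The concern.** Each score compares two lists, and either list can move between visits. A mismatch disappears if the patient starts following the prescription. It also disappears if the GP deletes a drug the patient was not taking, or adds one the patient was already taking. Only the first is a change in patient behaviour, and neither 1.4 nor 4.1.2 separates them.

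This would matter little if both arms' records were handled alike. But a structured comparison of record with intake, followed by a newly saved plan, is part of the intervention and absent from control. The reference against which adherence is judged therefore depends on the arm.

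The pilot is meant to screen further target variables for the main trial (1.4, further aims; 3.2; 12.2). A score that responds to list updating in one arm could look like a sensitive adherence measure and be carried forward as one.

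**Working it through.** **Inputs.** Score definitions and cut-offs come from 1.4: DIS flagged above 0.2; the others flagged below 0.8 or above 1.2. I read the bounds for DoS and RS as applying to those scores themselves, and the intake indicator d as 0 or 1. The protocol gives no discrepancy rate and no expected effect on adherence, so there is no stated figure to reproduce for this outcome. (The sample size, 20 practices × 5 patients = 100, is arithmetically right but does not rest on adherence.)

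**Formulas**, with n the number of listed prescriptions:

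- DIS = discrepancies / n
- DS = drugs taken / n
- DoS = Σ d·(actual dose / prescribed dose) / n
- RS = Σ d·(actual frequency / prescribed frequency) / n

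**Step 1: hold intake fixed and change only the list.** Doses and frequencies are as prescribed for every listed drug taken. An asterisk marks a flagged score.

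| Case | DIS | DS | DoS | RS |
|---|---|---|---|---|
| A, before: 8 listed, 2 not taken | 2/8 = 0.25* | 6/8 = 0.75* | 0.75* | 0.75* |
| A, after: the 2 drugs leave the list | 0/6 = 0 | 6/6 = 1.0 | 1.0 | 1.0 |
| B, before: 8 listed and taken, 2 unlisted drugs also taken | 2/8 = 0.25* | 10/8 = 1.25* | 1.0 | 1.0 |
| B, after: both added to the list | 0/10 = 0 | 10/10 = 1.0 | 1.0 | 1.0 |

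In A all four scores go from flagged to unflagged; in B two do. The patient takes the same drugs throughout. B assumes that a drug taken but not listed counts as a discrepancy in DIS, which the protocol does not state.

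**Step 2: hold the reference list fixed.** Against the T0 list, patient A stays at DIS 0.25 and DS, DoS and RS 0.75, all still flagged. The whole change in step 1 therefore comes from the list. Freezing the T0 list is not a remedy by itself, because it would count every agreed drug change as a discrepancy.

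**Step 3: illustration at group level.** Assume that each of n drugs is discrepant independently with probability p, that a share q of discrepancies is absorbed into the record, and that n does not change. The number remaining is then Binomial(n, p(1 − q)). For n = 5 and n = 8, DIS exceeds 0.2 when at least 2 remain. For n = 8, p = 0.2, q = 0: 1 − 0.8⁸ − 8·0.2·0.8⁷ = 0.497. With q = 0.5: 1 − 0.9⁸ − 8·0.1·0.9⁷ = 0.187.

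| n | p | DIS > 0.2, q = 0 | DIS > 0.2, q = 0.5 |
|---|---|---|---|
| 5 | 0.1 / 0.2 / 0.3 | 8.1% / 26.3% / 47.2% | 2.3% / 8.1% / 16.5% |
| 8 | 0.1 / 0.2 / 0.3 | 18.7% / 49.7% / 74.5% | 5.7% / 18.7% / 34.3% |

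Intake does not change in any cell. All values of p and q are assumed, so the table shows the direction and how widely the size can vary. It is not an estimate for this trial.

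**The case against.** A reader might infer that the intervention copies intake into the record, so that adherence improves by construction. The documents do not support that. Steps 5 and 7 have the GP review agreement, warnings and patient problems and then agree a plan. The outcome may follow intake, restore the earlier prescription or change both. Section 2.3 gives the purpose as more suitable and less complex medication that reflects the patient's perspective. The scores can improve for this reason; the protocol does not make it certain.

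Other points on that side have weight:

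- The Drug Score is already labelled as the doctor's over- or underestimate of intake, which is close to calling it record agreement. It is nevertheless filed and reported under adherence.
- The coded scores do not always move. With 5 listed drugs and 1 not taken, DIS is 0.20 and the others 0.80, none flagged even before any change. With 8 listed, 1 not taken and 2 unlisted drugs taken, DS goes from 9/8 = 1.125 to 9/9 = 1.00, inside the bounds both times. DIS at baseline in that patient is 3/8 = 0.375 if unlisted drugs count, but 1/8 = 0.125 and unflagged if they do not.
- The CRF list covers prescriptions and OTC products the doctor recommends, so a self-bought product need not enter the scored list.
- Control GPs also complete the medication CRF three times, have documentation training and receive the guideline. Their lists may change too, and zero change in control cannot be assumed.
- MARS and Morisky do not use the GP's record.
- Adherence to the currently agreed plan is a legitimate construct.

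The descriptive status of the analyses (12.2) and the reference to a later analysis plan do not dispose of the point. The protocol itself fixes formulas, cut-offs and label, and a descriptive comparison still misleads if the score does not measure what its label says.

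**Conclusion.** The point holds in a limited form. All four scores can improve with unchanged intake, the structured route to that improvement exists in the intervention arm only, and nothing in the protocol separates it from a change in patient behaviour. Only the direction of the possible bias is established. Its size is unknown, because it depends on how often patients' intake and records disagree, how GPs resolve the disagreement, how unlisted drugs are counted and how far control lists also change; the protocol gives none of these. Better agreement between record and intake may be a real benefit of the intervention; the fault is in reading it as adherence.

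The outcome is secondary and descriptive, so the pilot's primary comparison is untouched. The wording should still be changed, because these scores are candidates for the main trial.

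**What to change.** 1. In 1.4 and 4.1.2, name DIS, DS, DoS and RS as agreement between the GP's record and intake. State that a between-arm change in them alone will not be read as a change in patient adherence.
2. Using the CRF and telephone-interview lists from T0, T1 and T2 in both arms, classify every change in discrepancy as due to changed intake, changed record or both, and report the classes by arm. Include discrepancies that newly arise, also for newly agreed drugs. Counting only resolved baseline discrepancies would miss new non-adherence.
3. Base statements about patient behaviour on the intake component together with MARS and Morisky.
4. Report drugs taken but not on the doctor's list separately, and say whether they count in DIS.
5. Use one intake source in both arms. The synopsis names patient interviews, whereas 3.2 and 4.1.2 name the brown bag review, which 8.1 describes only as an intervention step. The telephone interview is held in both arms (1.6, 9.3.6.1). These sections must be reconciled.

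The cost is a change of wording and some extra coding of lists already collected, with no new data. The apparent adherence effect may become smaller.
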